
4.4 Exploratory Endpoint(s)/Outcome(s)

Secondary end-point analysis: biomarkers. In this sub-aim, we hypothesize that molecular biomarkers will change (improve) with each treatment phase, at least in part. Furthermore, we hypothesize that biomarkers may reveal (a) novel insight into therapeutic resistance and/or relapse; (b) reveal patient sub-groups not identified by histology; and (c) ultimately prove to be readily usable biomarkers in clinical settings and possess personalized medicine value. We will focus on molecular profiling of esophageal genes with the EoE Diagnostic Panel (EDP), a set of 94 mRNA transcripts that have been established to differentiate EoE from controls (e.g. GERD and normal

individuals), and to identify exposure and transcriptional signaling to SGCs²⁸. The EDP is typically performed on an extra biopsy taken from the distal esophagus²⁸. If our hypotheses are proven to be correct, they have potential to transform monitoring of patients during therapeutic intervention, by identifying molecular markers that have therapeutic significance, and also by reducing the need for biopsies, particularly after therapy is initiated. Essentially, the associated EDP algorithm renders the raw Ct. values of each embedded gene after real-time PCR in a way such that the upregulated genes and downregulated genes are summed up individually. A quantitative “EoE score” is derived from the Δ Ct. (normalized to GAPDH) summation to reflect disease severity and for statistical analysis. Utilizing different gene sets, EDP is also able to predict steroid exposure and remission status based on the same algorithm²⁸. In this case, the EoE score will be calculated at baseline endoscopy and in the posttreatment biopsies to assess change with treatment.

Secondary end-point analysis: Patient Reported Outcome (PRO) metrics. In this sub-aim, we hypothesize that therapeutic interventions will improve clinical symptoms as measured by PRO metrics. This is an important issue to resolve as only a few prior studies have shown the clinical efficacy of therapeutic interventions. In fact, several studies have shown dissociation between histology (eosinophil levels) and clinical improvement^{31,32}, but these studies have not used validated metrics for measuring symptoms. The measurement of pre/post diet symptoms using tools that have undergone at least some validation is a novel aspect of our study. While we have made substantial progress with the development and validation of a number of PRO measurements, there is still not agreement around the best measurements, related in part by the uncertainty of whether these instruments truly measure meaningful and accurate parameters. Agreement about these measurements has significant bearing on the eventual FDA approval of therapeutic agents³³. As such, we will take several approaches in this sub-aim. First, we will employ EoE specific measurement tools, including the adult EoE dysphagia questionnaire, EoE Adult Symptom Score Activity Index (EESAI), and the adult EoE quality of life score (EoE-QOL-A^{36,37,38,39}). In addition, we will also employ generic Health Related QOL metrics, such as PROMIS General Health Questionnaire, and eventually compare the changes in disease specific versus general health questionnaires. These PROs will be assessed at the screening visit and again at the end of each treatment phase to assess the effects of treatment.

AIM 2: To determine clinical parameters and biomarkers that predict responsiveness to therapies.

2a. Clinical phenotypes. In this sub-aim, we hypothesize that certain patient phenotypes will correlate with response to each intervention in the trial. We will assess the relationship between response to 1FED, 6FED, and SGC on age, height, weight, BMI Z-score, race, ethnicity, allergic status, participant compliance (defined by diet and SGC usage diaries), and screening eosinophil levels as readouts.

2b. Skin testing. In this sub-aim, we hypothesize that skin test results (prick testing to the 6 foods in the 6FED and atopy patch testing to milk) will provide significant predictive value for outcomes in the diet trial phases. While a substantial body of work has already been done concerning skin testing, there still remains

debate about its practice in managing EoE. As such, in this sub-aim, we will take several different approaches compared with prior work. In particular, we will be conducting a multi-site trial and have the advantage that we can standardize the skin testing procedure, by using agreed upon techniques, including food extracts, skin test reagents, and measurement parameters. We will thus be in a good position to dissect discrepant results between centers. Furthermore, our trial is unique in that half of the patients will undergo a milk elimination diet as part of the first phase. Thus, we will be in a position to focus on the value of skin testing for milk, which is particularly attractive as milk is the number one food trigger of EoE¹⁹. It is important to point out that although skin testing (including patch testing) is now readily performed in EoE, there have been no studies that have assessed the local response. For example, it has not yet even been determined if positive responses involve immunological reactions, so basic cytokine and histological analyses are likely to be fundamentally informative.

- 2c. Serum food specific IgE, CRD, and IgG4.** The level of food specific IgE, CRD, and IgG4 will be determined by a solid phase immunoabsorbent assay (ELISA) focusing on the 6FED foods. Serum will be banked and processed in batches. Component testing for at least each of the 6 foods will be performed as feasible. The Investigators reserve the right to perform these analyses using commercially available platforms including UniCAP and the Immuno Solid-phase Allergen Chip (ISAC, Thermo Scientific).
- 2d. Assessment of milk-driven T cells.** In this sub-aim, we will perform exploratory studies designed to test the presence and significance of circulating milk-specific T cells in EoE patients. We will test the hypothesis that milk-specific T cells will be primarily CD4+, IL-5+, IL-13+, consistent with prior work.⁴⁷⁻⁴⁹ Furthermore, we will test the sub-hypothesis that the level of milk-specific T cells will positively correlate with positive atopy patch tests to milk and the response rate to milk elimination (1FED and secondarily 6FED, which also contains milk). The frequency of Th2 cells will be determined by FACS analysis, and milk-specificity will be estimated by milk protein stimulation in vitro, particularly looking at CD154 induction, a marker of T cell activation. These exploratory studies, will be performed with shipped blood samples, by [name], as published.^{47,48,50,51} The study will be limited to a pilot analysis of patients who only enter the 1FED and we will compare patients with positive and negative skin tests (prick and patch).
- 2e. Predictive Biomarker-analysis of EoE transcriptome.** In this sub-aim, we aim to identify biomarkers that may predict responsiveness to any or all of the treatment interventions associated with this trial. Determining such a biomarker would have a profound effect on disease management as patients could be quickly triaged into different therapies, e.g. diet versus SGC; thus saving time, reducing the number of endoscopies and potentially improving quality of life issues. As such, in this sub-aim, we will perform the EDP analysis on baseline biopsies, focused on identifying transcript levels that differentiate patients that respond to each of the interventions. In preliminary studies, we have conducted this type of analysis on patients that recently participated in the randomized controlled trial of high dose fluticasone (1760 mcg per day) for the treatment of EoE. Forty-two participants were enrolled in this study (28 FP, 14 placebo). After 3 months, 65% of FP-treated and 0% of placebo-treated participants had complete remission ($P = 0.0001$); 12% of FP-treated and 8% of placebo-treated participants had partial remission. Of the FP-treated participants in complete remission, 73% continued in complete remission, and 20% were in partial remission after halving the daily FP dosage.⁵³

Baseline esophageal gene expression was compared between FP responders and non-responder patients by statistically screening two cohorts of samples before the FP exposure, namely the FP responders and FP-non-responders. A total of 15 genes (Figure 4 in the reference, $p < 0.05$, fold change > 2.0) on the EDP were identified with a tendency to predict subsequent FP efficacy with CR criteria (≤ 1 eosinophil/HPF in the distal esophagus). It is interesting to note that some of these transcripts include cardinal EoE transcriptome genes such as CCL26 (eotaxin-3) and periostin and CLC (Charcot-Leyden crystals, a marker of eosinophils) suggesting that elevated production was a positive prognostic factor for FP responsiveness; these findings are consistent with a recent report suggesting that more severe tissue inflammation including eosinophil levels was associated with FP responsiveness.⁵² This preliminary result highlights the potential ability of baseline molecular transcripts to differentiate patients but also importance of repeating this analysis with an independent cohort of FP treated patient samples, as preliminarily identified genes have not yet passed the false discovery rate (FDR) correction due to a relatively small n. It is expected that a replication cohort will bring in a higher power to pass the FDR filter. Meanwhile, multiple false-correction methods will be applied to the collective data set, such as the West-Young and Bonferroni methods.

2f. Elucidation of genetic components of EoE. In this sub-aim, we seek to elucidate the genetic components of EoE through the collection of blood and/or saliva for genetic analysis. Blood and/or saliva specimens will be obtained at one of the participants' study visits and will be used for DNA isolation. Blood will be drawn by a certified phlebotomist or an RN, LPN, DO, or MD. A standard protocol for collection of blood derived DNA will be utilized, and approximately 2 teaspoons (10 milliliters) of blood will be collected. If blood cannot be obtained or the subject elects to limit DNA collection to non-blood sources, an oral DNA specimen (saliva) will be obtained instead. Whether the sample collected is blood or saliva, samples will be deidentified, processed, and shipped to CCHMC for storage. DNA will remain available for future genetic testing.

4.5 End of therapy (EOT) and Follow-up

The primary efficacy endpoint (e.g. achievement of histologic remission of less than 15 eosinophils/HPF) will be determined at the end of phase 1 (week 6) at which time all participants will undergo EGD with biopsy. Participants who achieve histologic remission at the end of phase 1 will have completed the study and will resume follow-up care with their primary GI or Allergy physician. Participants whose disease remains active after being on 1FED and choose to continue into Phase 2 will continue on to 6FED in Phase 2. Participants whose disease remains active after being on 6FED in Phase 1 and choose to continue into Phase 2 will receive 6 weeks of SGC in Phase 2.

4.6 Stratification, Randomization, and Blinding/Masking

All eligible participants will be randomized 1:1 to either the 1FED or 6FED. Following this six week phase 1, all patients will undergo EGD with biopsy, and those whose disease remains active may choose to move on to Phase 2 (to either 6FED or treatment with swallowed SGC). The sponsor, investigator, study staff, and participant will all have knowledge of the treatment being received.

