4.2 Primary Endpoints

AIM 1: To determine the efficacy of a 1FED vs. 6FED in EoE.

- a. Primary end-point** The primary efficacy endpoint will be determined at the end of Phase 1 at which time all participants will undergo EGD with biopsy and the percentage of patients who have <15 peak eosinophils/hpf will be determined. The slides will be reviewed by local pathologists for clinical purposes, who will be blinded to the treatment group. The Central Review Pathology Committee (CRPC), who will also be blind to the treatment group, will also review the slides, and the peak eosinophil count from this CRPC review will be used to determine whether or not participants are eligible to continue into Phase 2 of the study. Participants with ≥ 15 peak eosinophils/hpf who were on 6FED during Phase 1 and choose to continue into Phase 2 will receive SGC for six weeks while on an unrestricted diet. Participants with ≥ 15 peak eosinophils/hpf who were on 1FED during Phase 1 and choose to continue into Phase 2 will maintain the 6FED therapeutic diet for 6 weeks. The CRPC will subsequently review the esophageal biopsy slides to determine other parameters (such as the Histology Scoring System (HSS)). CRPC review will be completed, whenever possible, within 2 weeks of a subject's endoscopy. Participants who achieve histologic remission at the end of Phase 1 (as determined by CRPC review) or who complete Phase 1 and opt out of Phase 2 will have completed the study and will resume follow-up care with their primary gastroenterologist or allergist.

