13.3 Measures to Minimize Bias

Patients will be randomized using a 1:1 scheme to 1FED or 6FED within each investigative site. Study staff will remain blinded to the randomization plan so they do not know the upcoming treatment assignment will be for a patient until after the patient has been assigned. Study personnel who will perform the histologic assessments will be blinded to treatment assignment for the slides they are evaluating. The CRPC will not be told which diet a

participant has been assigned to, and they will not receive any information or documentation indicative of dietary assignment. The slides and/or images of slides provided to the CRPC will not contain any information that reveals which diet the participant is on. Knowledge of dietary assignment will be limited to study staff who need to know which diet a participant has been assigned to (i.e. dietitians).

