13.4.4 Analyses of Secondary and Other Endpoint(s)/Outcome(s)

Following are the secondary objectives of the study:

1. To extend Phase 1 of this study with a prospective non-blinded trial that determines the rate of remission following SGC in the 6FED non-responders and the rate of remission following 6FED in the 1FED non-responders (Phase 2).
2. To evaluate the effect of each therapy on histological remission defined by a variety of changes in eosinophils, including (a) pre- and post-therapy peak eosinophil counts; (b) partial remission (2-14 peak eosinophils/hpf); and (c) complete histological remission (≤ 1 peak eosinophils/hpf).
3. To evaluate the effect of each therapy by utilizing the histology scoring system (HSS) created to express the severity and extent of other abnormalities in the gastrointestinal (GI) tract that often accompany eosinophilic inflammation.
4. To evaluate endoscopic outcomes as assessed by the endoscopy scoring system (EREFS).
5. To determine the impact of each therapeutic intervention on biomarkers using the EoE Diagnostic Panel (EDP).

For secondary objective 1, the remission rate for non-responders who proceed to Phase 2 will be summarized separately depending on the treatment patients received during Phase 1. The 95% two-sided confidence interval for the rate will be provided. In addition, forest plots that display the estimated remission rate along with two-sided 95% confidence interval will be presented for the subgroups as defined for the primary endpoint. This will provide a visual representation to assess consistency of rates across subgroups. If the remission rate is missing for patients in Phase 2, it will be imputed as a treatment failure.

The formal statistical hypothesis for each of the key secondary endpoint is:

$$H_0: \theta_{1FED} = \theta_{6FED}$$

$$H_1: \theta_{1FED} \neq \theta_{6FED}$$

where

θ_{1FED} =population parameter (e.g. mean, proportion) for patients in histologic remission (<15 eosinophils/hpf) on the 1FED diet at end of Phase 1

θ_{6FED} =population parameter (e.g. mean, proportion) for patients in histologic remission (<15 eosinophils/hpf) on the 6FED diet at end of Phase 1.

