- 3) Histology Scoring System (HSS): Will include the overall score, grade score, stage score, and the inflammatory and structural sub-scores. Scores will be reported as distal, proximal, and maximum
- 4) HSS score by remission status (complete, partial, and no remission).
- 5) Endoscopy Scoring System (EREFS): Will include the overall score and the inflammatory and fibrostenotic sub-scores. Scores will be reported as distal, proximal, and maximal score.
- 6) EoE Diagnostic Panel (EDP): The summary EoE score (EDP total score) will be a secondary outcome.

Derived Variables.

- 1) HSS scores. Sum of the feature scores divided by the maximum possible score for the biopsy for grade and stage. The total score is the sum of the grade and stage scores. Inflammatory sub-scores include the following features: eosinophils, abscesses, surface layering, and surface necrosis. Structural sub-scores include basal layer hyperplasia, dilated intercellular spaces, apoptotic epithelia, and lamina propria fibrosis.
- 2) HSS remission. HSS remission is defined as a having both a grade and stage total score less than or equal to 3 and an eosinophil grade score no greater than 1. This is calculated separately for distal and proximal biopsies. When both distal and proximal biopsies are in remission, this is considered complete remission, when only one of the two biopsies meet these criteria, it is partial remission. When neither meet these criteria, it is no remission. Analyses will include full remission vs other and full+partial remission vs no remission.
- 3) EREFS. Total EREFS score will be calculated by summing the grades for all five of the features. The inflammatory score contained the sum of the exudate, edema, and furrows scores (this could range from 0 to 5), and the fibrostenotic score contained the sum of the rings and stricture scores (this could range from 0 to 4).
- 4) Adherence. Adherence will be dichotomized into mostly adherent vs not-mostly adherent. The judgement of adherence will be based on questionnaires about food intake and dietitian input. If inconsistent, food diaries will be reviewed. The final adherence call will be provided to the statistician.
- 5) Atopy. Atopy is a multi-faceted disease. Individuals will be defined as atopic if they report a history of asthma, eczema, allergic rhinitis, allergic conjunctivitis, IgE mediating food allergy

and/or atopic dermatitis.

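### Protocol 4.6 and 13.3 disagree on who knows the diet, and neither document names or masks the EREFS rater, so one formally tested secondary endpoint is open to assessor bias

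*Protocol*

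**What the plan says.** Two current sections of the protocol describe who knows the assigned diet.

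- Section 4.6 (Stratification, Randomization, and Blinding/Masking): "The sponsor, investigator, study staff, and participant will all have knowledge of the treatment being received". It makes no exception for any outcome assessor.
- Section 13.3 (Measures to Minimize Bias): "Knowledge of dietary assignment will be limited to study staff who need to know". Dietitians are the only role it names.

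Masking of outcome assessment is stated only for histology. Section 4.2 says of local review: "The slides will be reviewed by local pathologists for clinical purposes, who will be blinded to the treatment group". It says the same of central review: "The Central Review Pathology Committee (CRPC), who will also be blind to the treatment group". Section 13.3 adds: "Study personnel who will perform the histologic assessments will be blinded to treatment assignment for the slides they are evaluating".

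EREFS is secondary objective 4 in protocol 13.4.4: "To evaluate endoscopic outcomes as assessed by the endoscopy scoring system (EREFS". The SAP lists it as secondary outcome 5 under Variables of Interest: "Will include the overall score and the inflammatory and fibrostenotic sub-scores". Protocol 13.4.4 and the SAP section on secondary endpoints both compare the arms on it at the end of Phase 1 at two-sided alpha 0.01. Neither document names the rater, masks the rater or provides for central reading of endoscopic images. The SAP calls the trial non-blinded but says nothing about masking of assessors.

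**The concern.** A site that follows 4.6 may tell all its staff the diet. A site that follows 13.3 would tell only the dietitians. Practice could therefore differ between sites, with each able to point to the protocol.

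The gap matters for EREFS because it grades what the rater sees at endoscopy, so knowledge of the arm can influence the grade. The protocol's own hypothesis is directional: section 3.1 expects 6FED to be superior. Open participants are unavoidable in a diet trial, but open assessors are not, and 13.3 shows that the sponsor meant to limit who knows. At stake is whether a between-arm difference in EREFS can be read as an effect of the diet or partly as an effect of the rater's expectation.

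**Working it through.** **Text comparison, by role**

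| Role | Section 4.6 | Section 13.3 | Other text |
|---|---|---|---|
| Participant | knows | not addressed | – |
| Sponsor | knows | not addressed | – |
| Dietitian | knows (as study staff) | knows | – |
| Investigator, other study staff | know | only if they need to | – |
| Local and central pathologists | no exception stated | blinded | blinded (4.2) |
| EREFS rater | not named | not named | not named in the SAP |

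Three points follow.

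1. For the investigator and for staff other than dietitians, 4.6 and 13.3 cannot both hold as written.
2. Section 13.3 also says staff are blinded to the randomization plan. That sentence concerns concealment of upcoming assignments, so it does not mask outcome assessment.
3. Section 6.5 treats the endoscopies as standard of care and not as study procedures. The endoscopist may therefore fall outside the term study staff, in which case neither section governs that person. Masking is then undefined, not assured.

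**Illustration of size**

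The plan gives no figure to reproduce here: the documents state no SD for EREFS and no expected scoring bias. Inputs:

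- n = 68 per arm (protocol 13.6).
- Two-sided alpha 0.01, critical value 2.576 (protocol 13.4.4; SAP).
- Scale 0 to 9, from the SAP's sub-score ranges of 0–5 and 0–4 (5 + 4 = 9).
- SD 1.5, 2 or 2.5 points: **assumed**.
- Differential scoring shift between arms of 0.25 or 0.5 point, with no true difference: **assumed**.

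Formulas: SE = SD × √(2/68) = SD × 0.1715, and P(false positive) ≈ Φ(shift/SE − 2.576). The opposite tail is below 0.1% in every case and is left out.

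| SD | SE | Shift 0.5 | Shift 0.25 |
|---|---|---|---|
| 1.5 | 0.257 | Φ(1.944 − 2.576) = 26% | Φ(0.972 − 2.576) = 5% |
| 2.0 | 0.343 | Φ(1.458 − 2.576) = 13% | Φ(0.729 − 2.576) = 3% |
| 2.5 | 0.429 | Φ(1.166 − 2.576) = 8% | Φ(0.583 − 2.576) = 2% |

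With 60 per arm, the protocol's number before the drop-out allowance, the 0.5-point column becomes 23%, 11% and 7%. This is a simple two-sample approximation; the planned mixed model with covariates would give somewhat different values.

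**The case against.** The trial is openly declared non-blinded, so 4.6 may be no more than a loose general sentence. It cannot be fully literal, since pathologists are blinded elsewhere. Section 13.3 is the more specific rule and, read strictly, already keeps the diet from any study endoscopist. This stands in part: it shows the likely intent, but a site reading 4.6 alone has clear permission to do otherwise, and 13.3 does not reach a rater who is not study staff.

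No passage says that the endoscopist scores EREFS. That stands. It is a reasonable inference for a score of endoscopic appearance, but the supported statement is that both the rater and the rater's masking are unspecified.

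A reader might infer that the primary endpoint is also biased, because the peak count depends on where tissue is taken. The documents do not support that. All slide reading is blinded, and the peak is taken over the whole esophagus (section 1). The endoscopist's discretion in 6.4.4 concerns additional research biopsies and is presented as a way to reduce risk. Blinded reading could not undo selective sampling, so the route is possible, but nothing in the plan indicates that it would operate and it cannot be quantified.

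The error rates rest on assumed inputs. That also stands: the result is driven by the shift, for which the documents give no value.

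**Conclusion.** The inconsistency between 4.6 and 13.3 is real, and the missing statement on the EREFS rater is a genuine gap for an endpoint tested at alpha 0.01. The consequence is that the rater may know the arm. A reader might conclude that the rater will know it, or that the false-positive rate will be 8–26%; the documents establish neither. Those figures, and the 2–5% for the smaller shift, show only how sensitive the test would be if a shift of that size occurred under the assumed SDs.

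The reach is one secondary endpoint. Reading of the primary endpoint is protected. This is an inexpensive improvement worth making and does not threaten the main comparison. It rests on the text of the two sections and on the inference that EREFS is scored by someone present at the endoscopy.

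**What to change.** 1. Reconcile 4.6 with 13.3 role by role. Keep the statement that participants and dietitians know the diet, and say explicitly which of the sponsor, investigator and other staff do. Replacing the 4.6 sentence wholesale with the 13.3 rule would leave the participant, sponsor and investigator unaddressed.
2. State in the protocol and the SAP who scores EREFS, and that this person is not told the diet before scoring and taking biopsies.
3. Record at each endoscopy whether the rater knew the diet.
4. Where masking fails, because the investigator performs the endoscopy or the participant discloses the diet, report EREFS as an open-label assessment. Treat any comparison restricted to masked ratings as descriptive: that subset is formed after randomisation, and unmasking may be more frequent in one arm.

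The cost is protocol and SAP wording plus one field on the case report form, with no extra staff. The drawback is that masking will be incomplete at some sites, so there the change documents the problem without removing it.
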